3. Determine whether CBZ treatment reduces portal pressure in AT-deficient patients with severe liver disease as assessed by serial hepatic venous pressure gradient measurements
4. Determine whether CBZ treatment is safe and tolerated by patients with severe liver disease caused by AT deficiency
5. Determine whether CBZ treatment leads to stabilization in disease severity as measured by the MELD scores

STUDY DESIGN (See also Study Flow Chart in Attachment 2)

This is a Phase II prospective study of the use of CBZ in adolescents and adults with AT deficiency and compensated cirrhosis. It is a randomized, double-blinded, placebo-controlled study in which 20 subjects will receive drug and 10 subjects will receive placebo. Eligible patients will take CBZ or placebo for 12 months. Transvenous catheterization of the hepatic vein for measurement of hepatic venous pressure gradient will be carried out before and after the treatment period. Liver biopsies will be carried out through the transvenous catheterization at the same time to obtain liver tissue for measurement of hepatic ATZ load and hepatic fibrosis. These studies are often done as a part of standard of care for adults with cirrhosis. Clinical and biochemical follow-up will be undertaken to assess safety and tolerability of CBZ in these patients. After 12 months of therapy, HVPG and transvenous biopsies will be repeated permitting a formal assessment of effects on ATZ load (by PAS staining, immunostaining, and immunoblot analysis) and fibrosis (by quantitative Sirius red staining and by examination of changes in HVPG). This approach has been effectively utilized to demonstrate efficacy of antiviral therapy in both Hepatitis C and Hepatitis B in reducing portal pressure.

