16. WBC <1,500
17. Platelets <25,000
18. Inability to take oral medication
19. Status post Transjugular Intrahepatic Portosystemic Shunt (TIPS) or scheduled to undergo during trial participation

STUDY DRUG AND DRUG MANAGEMENT:

Rationale for Placebo Control:

The placebo group is designed to provide control for the effects of sample error and variability. This variability could affect liver biopsy as well as HVPG measurements and the placebo control is particularly important because of the relatively small number of subjects in the trial. In addition, the placebo control may provide insight into the tolerability of CBZ by providing natural history data for complications of AT deficiency-associated cirrhosis. Placebo will be prepared by the UPMC Investigational Drug Service (IDS) in capsules that are identical to those of the active compound CBZ.

Randomization:

Once it is determined the patient is eligible for the clinical trial, the patient will be randomized to receive a study medication that will be CBZ, the active medication, or a placebo that will appear similar to but not contain the active medication. Patients will be randomized 2:1 (CBZ: Placebo) with two patients receiving CBZ for every one patient receiving placebo. Patients will be further stratified by ongoing treatment with non-selective beta-blockers used for portal hypertension (e.g. propranolol, nadolol or carvedilol). If the patient is receiving any dose of nonselective beta-blocker prior to study entry, this may decrease portal hypertension which in turn should be associated with decreased HVPG. We want to ensure that both treatment and placebo arms have an equal number of patients receiving nonselective beta-blocker and do not plan to alter this therapy during this investigation.

The Investigational Drug Service will provide subjects with study medication sufficient to last until the next visit + 5 days extra. The UPMC Investigational Drug Service (IDS) will use Medi-dose cups for dispensing CBZ/placebo capsules, depositing one dose of medication/placebo (two capsules) in each Medi-dose cup. UPMC Investigational Drug Service (IDS) will seal and then label the Medi-dose cup with the subject's ID number and the dose of medication (or placebo). IDS will be responsible for delivering the

A Preliminary Study of the Efficacy and Safety of Carbamazepine in Severe Liver Disease Due to Alpha-1 Antitrypsin Deficiency

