Medi-dose cups to subject's home address via UPS overnight shipping, and storing the remaining of the Medi-dose cups.

A Study Monitor (see below) will be the only members of the investigative team that is not blinded because the Study Monitor will be responsible for adjustments in CBZ dosage based on drug levels. The Study Monitor will consult with the sponsor-investigator and/or physician sub-investigators to determine exactly how to adjust the dosage but these consultations will be carried out without revealing the identity of the patient.

Administration and Drug Accountability:

CBZ/placebo will be administered at a maximum dose of 1200 mg/day orally for 12 months for subjects over 15 years of age and at a maximum dose of 1000 mg/day for subjects less than 15 years of age. This will involve twice daily dosing with a combination of 100 mg-extended release tablets. Extended release tablets are better tolerated, have a narrow fluctuation in drug concentration, and fewer central nervous system complications than immediate-release formulations (43). To reduce the likelihood of hypersensitivity reactions the subjects will be started on 400 mg/day in 2 doses and the dose will be increased weekly by 200 mg per day until reaching a dose of 1200 mg/day (or 1000 mg/day in subjects less than 15 years of age). A subject's dose escalation may be adjusted if deemed appropriate by the sponsor-investigator or principal investigator but it will not exceed a weekly 200 mg per day increase. Drug levels will be monitored beginning at the 4 week visit, then at each study visit to ensure that the therapeutic concentration of 4-12 ug/ml is reached but not exceeded and then maintained. CBZ will be administered orally twice a day using extended release tablets. The Study Monitor will review the results of the blood level measurements following each visit and use that information for adjustment of the dose of CBZ to maintain the therapeutic drug level. The Study Monitor will not be a member of the investigative team involved with direct patient management. The Study Monitor will not be blinded. To maintain the blinding that is essential to the study design, the Study Monitor will not communicate the actual blood level result to the subject, the subject's physician or to the sponsor-investigator team.

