-If study drug has been stopped for more than 2 weeks, the sponsor-investigator along with principal investigator will determine both the dose with which the subject restarts and the appropriate dose escalation schedule.

Carbamazepine (study drug) or placebo dose alteration:

The dose of the study drug will be altered based upon the schedule below. Only the study monitor will know the serum trough level and only the study monitor will make dose adjustments for changes in the blood level. The Sponsor-Investigator and/or sub-investigators will be responsible for making adjustments in the dose of Study Medication based upon the clinical and biochemical results outlined below. If these individuals determine that the dose of study drug needs to be adjusted, the request will be made to the Study Monitor who will in turn contact the IDS to carry out the change in dose. When a dose alteration is made based on findings other than the trough blood level, comparable dose reductions will not occur in patients receiving placebo.

1. Serum trough level ≥ 12 $\mu\text{g/ml}$ (to be performed ONLY by the study monitor) See algorithm.

2. (Serum trough level ≤ 4 $\mu\text{g/ml}$ (to be performed ONLY by the study monitor)(study monitor may elect to order a repeat trough level before making a change in dosage)
 - a. No change in protocol unless prior dose reduction.

A Preliminary Study of the Efficacy and Safety of Carbamazepine in Severe Liver Disease Due to Alpha-1 Antitrypsin Deficiency

- b. If a prior dose reduction has been made by the study monitor based upon clinical or biochemical abnormality, the dose of the study medication will not be increased unless there is resolution of the clinical or biochemical finding. Increase in dose cannot be made if subject is already on dose of 1200 mg/day or, if less than 15 years of age, on a dose of 1000 mg/day
 - c. Continue “b” until trough level is in the therapeutic range

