2. WBC <1,000
 - a. Decrease dose by 50%
3. Neutrophil count <500
 - a. Decrease dose by 50%
4. Platelets < 20,000
 - a. Decrease dose by 50%
5. ALT > 500 IU/dl
 - a. Decrease dose by 50%
6. INR \geq 1.8 not corrected by 5 mg of vitamin K
 - a. Decrease dose by 50%

Guidelines for subsequent Study drug dose adjustments

Indications to discontinue CBZ

1. Child-Pugh score > 12
2. Hepatic encephalopathy uncontrolled with outpatient medical therapy
3. Total bilirubin > 7 mg/dL
4. Evidence of anticonvulsant hypersensitivity syndrome
 - a. Fever > 38.5 and
 - b. Lymphadenopathy, and
 - c. Erythematous, maculopapular, pruritic, or exfoliating rash
5. WBC <1,000 despite 2 weeks of Carbamazepine dose reduction, may resume therapy at 50% of starting dose when WBC > 3,000
6. Neutrophil count <500 despite 2 weeks of Carbamazepine dose reduction, may resume therapy at 50% of starting dose when ANC > 1,500
7. Platelet count <20,000 despite 2 weeks of Carbamazepine dose reduction, may resume therapy at 50% of starting dose when plt > 40,000
8. Hgb <8.5 mg/dl
9. INR \geq 2.5 not corrected by 5 mg of Vitamin K

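### The protocol does not say whether placebo subjects receive nominal dose changes, and with the dose printed on every cup one reading of the rule would unblind

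*Combined protocol and SAP*

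**What the plan says.** All references are to the combined protocol and SAP.

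- **Study Design:** "It is a randomized, double-blinded, placebo-controlled study in which 20 subjects will receive drug and 10 subjects will receive placebo". The section on administration and drug accountability calls the blind essential. Only the Study Monitor is unblinded.
- **Randomization (dispensing paragraph):** the pharmacy puts one dose, two capsules, in each cup and labels it with the subject's "ID number and the dose of medication (or placebo"). Cups go to the subject's home. Under Assessment of adherence, unused medication comes back at each visit for pill counts.
- **Carbamazepine (study drug) or placebo dose alteration:** two routes lead to a change. The Study Monitor alone acts on trough levels. The blinded sponsor-investigator or sub-investigators act on clinical and laboratory findings, and for these "the request will be made to the Study Monitor who will in turn contact the IDS to carry out the change in dose".
- **Same section, on the second route:** "When a dose alteration is made based on findings other than the trough blood level", "comparable dose reductions will not occur in patients receiving placebo".
- **List of triggers that follows:** for white cells, neutrophils, platelets, ALT and INR the instruction is "Decrease dose by 50" per cent.

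**The concern.** An investigator who asks for a reduction knows which subject it is for. If the request is carried out on CBZ but not on placebo, the next labelled cup shows the arm to the subject, and staff can see it when cups are returned.

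The people who would learn the arm also make the judgements most open to bias. The sponsor-investigator may request reductions and also judges whether each adverse event is related to the drug. Investigators decide on temporary holds. Ascites and encephalopathy, both graded clinically, enter the Child-Pugh score, which is a ground for discontinuation. Objective 4 (safety and tolerability) is therefore directly exposed. Discontinuation and withdrawal in turn affect who provides a week-52 biopsy, from which the primary outcome is read.

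**Working it through.** The plan gives no figure on this point, so there is none to reproduce. The check is mainly a comparison of the text, with one illustration.

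**1. Can a placebo subject meet a clinical trigger?** Yes. Subjects with an INR up to 2.2 may enter, while an INR of 1.8 or more that vitamin K does not correct is a reduction trigger. The section on specific adverse events also expects raised ALT and INR and low counts at baseline. Disease alone can bring a placebo subject to a trigger.

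**2. What happens then?** Two readings fit the sentence.

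- *Reading A:* when one subject is reduced, no matched sham reduction is made in a different placebo subject. A placebo subject who meets a trigger is still nominally reduced on request. Requests are made blind, so a clinical reduction reveals nothing.
- *Reading B:* a placebo subject who meets a trigger is not reduced. After a request, a changed label means CBZ with certainty and an unchanged label means placebo with certainty.

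**3. Do the stated safeguards close reading B?** No. Identical capsules and withheld level results do not hide a printed dose. The consultations held without patient identity concern the Study Monitor's level-based adjustments; in the clinical route the investigator starts the request and knows the subject. Release of the arm is otherwise limited to safety need, and the label would bypass that control.

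**4. Level-driven changes.** "the Study Monitor will be responsible for adjustments in CBZ dosage based on drug levels". A trough at or above 12 µg/ml can arise only on CBZ. A placebo sample would fall at or below 4 µg/ml, where the rule is no change unless the dose was reduced earlier. So the natural trigger for a level-driven reduction exists only on CBZ. Whether placebo subjects get matching nominal changes is not stated in the visible text.

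**5. Illustration.** Let r be the probability that a CBZ subject has a visible dose change and q the same for placebo. With 2:1 allocation:

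P(CBZ | change) = 2r / (2r + q)

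- q = r (full mirroring): 2r / 3r = 0.67, the same as the prior 20/30.
- q = r/2: 2r / 2.5r = 0.80.
- q = 0: 2r / 2r = 1.00.

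These values do not depend on r. The number of CBZ subjects affected does: expected number = 20r, and P(at least one) = 1 − (1 − r)^20.

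| r | Expected of 20 | P(at least one) |
|---|---|---|
| 3% | 0.6 | 0.46 |
| 10% | 2 | 0.88 |
| 20% | 4 | 0.99 |
| 30% | 6 | >0.99 |

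The 3% is the protocol's figure for dose reduction because of side effects in general CBZ use. The 10–30% range is assumed.

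The absence of a change tells little: P(CBZ | no change) = 2(1 − r) / [2(1 − r) + (1 − q)], which at r = 20% and q = 0 is 1.6 / 2.6 = 0.62. An unchanged label is informative only after a request that should have changed it.

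**The case against.** The best defence is that reading A is the natural one. The section heading covers placebo as well as study drug, investigators request changes to the study medication without knowing the arm, and the Study Monitor has the pharmacy carry the change out. A blinded request needs no sham elsewhere, so the sentence may only be saying that. This stands as a possible reading, but the text does not state it, and the Study Monitor and pharmacy must act on the sentence as written.

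A changed label is also not in itself a signal. Labelled doses change during the weekly escalation, which investigators may adjust, and again on restart after an interruption of more than five days, in both cases with no distinction by arm. Repeat draws are not peculiar to CBZ either, since any subject returns if a sample was not at trough. All of this stands. It limits what can be learned from an isolated change, but not from an unchanged label after a request.

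Three stronger conclusions are tempting, and the documents do not support them.

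- *Level-driven changes occur only on CBZ.* Only the natural trigger is confined to CBZ. The no-mirroring sentence is limited to findings other than the trough level, which by contrast suggests that level-driven changes may be matched on placebo. The algorithm it refers to for high levels is not shown in the available text and cannot be counted as missing.
- *There are 100 unblinding occasions on CBZ and none of 50 on placebo.* Five level visits × 20 and × 10 subjects count blood draws, not dose changes. The week-52a draw can hardly lead to a later visible change, which leaves 20 × 4 = 80 on CBZ, and a low level normally leads to no change. The zero assumes the very point in doubt.
- *MELD is biased through clinical scoring.* MELD is built from bilirubin, creatinine and INR. It is touched only through who stays in the study.

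**Conclusion.** The point holds as an unresolved ambiguity with a real consequence. It is not a demonstrated break of the blind. Under reading B, every clinical request followed by a look at the label reveals the arm; under reading A none does. For level-driven changes, the risk depends on a placebo procedure that the visible text does not describe.

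The size cannot be fixed from the documents. The certainty about the arm after a dose change runs from 0.67 with full mirroring to 1.00 with none. The number of CBZ subjects concerned runs from 0.6 of 20 at the general-use rate to 2–6 of 20 at the assumed 10–30%. This rests on the 2:1 allocation, on the label being seen, and on those assumed rates.

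The exposure is to causality assessment and tolerability under objective 4 and to discretionary holds and withdrawals, and hence to who reaches the biopsy. Many withdrawal criteria are laboratory thresholds and the primary outcome is a histological count, which limits the effect on efficacy. The sentence should be corrected, because one permitted reading defeats a blind that the protocol itself calls essential.

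**What to change.** Reconcile the dose-alteration section with the dispensing and Study Monitor text in three steps.

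1. Replace the no-mirroring sentence with one to this effect: *any dose change requested by blinded investigators is carried out nominally and in the same way for every subject, whichever the arm.*
2. State what placebo subjects receive when level-driven changes occur on CBZ, and that the Study Monitor directs it.
3. Replace the printed dose with a coded label whose key the pharmacy holds, keeping the two-capsule cup already described. The code should change at every dispensing, so that a new code carries no information. This step protects the blind under either reading.

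The cost is a short protocol amendment, a revised pharmacy instruction and a little extra pharmacy work. Sham blood draws are not needed. No planned sample size or analysis changes, and no dose or clinical threshold is proposed here.

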2. WBC <1,000
 - a. Decrease dose by 50%
3. Neutrophil count <500
 - a. Decrease dose by 50%
4. Platelets < 20,000
 - a. Decrease dose by 50%
5. ALT > 500 IU/dl
 - a. Decrease dose by 50%
6. INR \geq 1.8 not corrected by 5 mg of vitamin K
 - a. Decrease dose by 50%

Guidelines for subsequent Study drug dose adjustments

Indications to discontinue CBZ

1. Child-Pugh score > 12
2. Hepatic encephalopathy uncontrolled with outpatient medical therapy
3. Total bilirubin > 7 mg/dL
4. Evidence of anticonvulsant hypersensitivity syndrome
 - a. Fever > 38.5 and
 - b. Lymphadenopathy, and
 - c. Erythematous, maculopapular, pruritic, or exfoliating rash
5. WBC <1,000 despite 2 weeks of Carbamazepine dose reduction, may resume therapy at 50% of starting dose when WBC > 3,000
6. Neutrophil count <500 despite 2 weeks of Carbamazepine dose reduction, may resume therapy at 50% of starting dose when ANC > 1,500
7. Platelet count <20,000 despite 2 weeks of Carbamazepine dose reduction, may resume therapy at 50% of starting dose when plt > 40,000
8. Hgb <8.5 mg/dl
9. INR \geq 2.5 not corrected by 5 mg of Vitamin K

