14. WBC <1,500
15. Platelets <25,000
16. Inability to take oral medication
17. Status post Transjugular Intrahepatic Portosystemic Shunt (TIPS) or scheduled to undergo procedure during trial participation

Screening visits:

At the screening visits a complete history and physical examination will be performed. Screening blood tests will be obtained to assess liver function and to verify the Child Pugh status. A pregnancy test will be done. AT phenotyping and absence of the genetic markers HLA-A*3101 and HLA-B*1502 will be confirmed. Potential subjects will be screened with the Personal Health Questionnaire-9 (PHQ-9). The PHQ-9 has been used successfully to screen adolescents over 13 years of age and adults (39). Subjects will be excluded if scoring 10 or higher on PHQ-9. An abdominal sonogram with Doppler will be performed to assess patency and directional flow of the portal and hepatic veins. Once these studies are confirmed as being consistent with the eligibility criteria arrangements will be made for the pre-treatment HVPG measurement (see below). The hepatic venous pressure gradient measurement and liver biopsy are done together as a single procedure using the transvenous route. Intravenous conscious sedation is used to carry out the procedure. Subjects will receive fresh frozen plasma if the INR >1.6 and platelet transfusion if the platelet count is <50,000 prior to the procedure to prevent bleeding as per usual clinical practice. Subjects will be carefully monitored during the procedure and in the recovery room after the procedure.

Screening Hepatic venous pressure gradient:

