CBZ may interact with other anticonvulsants, including half-life shortening when given with phenobarbital, phenytoin and primidone and half-life prolongation with valproate. Several drugs inhibit the elimination of CBZ and therefore elevate its serum levels, including erythromycin, isoniazid, triacetyloleandomycin, destropoxyphene, viloxazine, nicotinamide, verapamil and diltiazem. CBZ itself can affect the serum concentrations of other drugs, including valproate, ethosuximide, doxycycline, clonazepam, haloperidol, phenytoin and warfarin.

These drug interactions may necessitate changes in dose of CBZ or other drugs but do not prohibit the use of CBZ or other drugs while administering CBZ. These changes will be directed by the Sponsor-Investigator or sub-investigators.

ADVERSE EVENTS AND TOXICITY MANAGEMENT

Subjects will be closely monitored for the major side effects of CBZ, including allergic reaction, sedation, and bone marrow depression as well as for hepatotoxicity that could worsen the liver disease. This will include history, clinical examination and laboratory testing. Monitoring will be carried out at each study visit. In general it will not be necessary to reduce the dose of CBZ or discontinue CBZ unless there is an obvious allergic reaction, progressive hematological toxicity that includes aplastic anemia, neutropenia and/or thrombocytopenia, progressive hepatic toxicity with rising transaminases, decreasing albumin levels or prolongation of the prothrombin time, unremitting sedative effect, or CBZ levels in the toxic range.

In the event that a subject temporarily discontinues drug for any reason OR an investigator determines the a subject should temporarily hold study drug due to a clinical reason, we will reinitiate therapy based upon the following parameters;

A Preliminary Study of the Efficacy and Safety of Carbamazepine in Severe Liver Disease Due to Alpha-1 Antitrypsin Deficiency

-If study drug has been stopped for less than or equal to 5 days the subject will resume taking the previous dose.

[figure not shown]
-If study drug has been stopped for more than 5 days but less than or equal to two weeks, the subject will resume half of the previously assigned dose (if half the previous dose is unavailable, the next available formulation close to but less than half the previous dose is acceptable) for one week and return to the full previous dose 7 days later.

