Subjects will be excluded if they have evidence of an additional potential cause of active liver disease (e.g. infectious hepatitis, alcohol related liver disease, Wilson disease, sclerosing cholangitis, primary biliary cirrhosis). Subjects will also be excluded if they have very severe liver disease (Child-Pugh score greater than or equal to 12; serum bilirubin > 5; INR > 2.2; hepatic encephalopathy uncontrolled with outpatient medical therapy), severe renal disease (serum creatinine > 1.5 mg/dl), alcohol intake > 30 gms/day, evidence of hepatobiliary malignancy, pregnancy/lactation, portal vein or splenic vein thrombosis, severe cardiac or pulmonary disease felt to be a contraindication to CBZ therapy, HLA-B*1502-positivity, HLA-A*3101-positivity, history of suicide attempt, potential for suicide behavior based on pre-treatment screening test, severe leucopenia (wbc count < 1,500) or thrombocytopenia (platelet count < 25,000).

Total Duration of Therapy: 12 months

Forms to Complete: Informed consent signed by patient and or parent/legal guardian; entry data; visit follow up data; final report

Endpoints of the study:

1. Change in hepatic load of ATZ.
2. Change in degree of hepatic fibrosis.
3. Change in HVPG.
4. Ability to tolerate long-term course of CBZ without adverse events.

Reimbursement for study participation: Only financial assistance to cover travel related expenses.

A Preliminary Study of the Efficacy and Safety of Carbamazepine in Severe Liver Disease Due to Alpha-1 Antitrypsin Deficiency

Literature Cited

1. Perlmutter D.H., Alpha-1-Antitrypsin Deficiency, in Schiff's Disease of Liver, Schiff E.R., Maddrey W.C., Editor. 2007; Lippincott-Raven: Philadelphia. 1063-1084.
2. Perlmutter, D.H., Pathogenesis of chronic liver injury and hepatocellular carcinoma in alpha-1-antitrypsin deficiency. *Pediatr Res*, 2006; **60**: 233-8.
3. Perlmutter D.H., Autophagic disposal of the aggregation-prone protein that causes liver inflammation and carcinogenesis in alpha-1-antitrypsin deficiency. *Cell Death Differ*, 2009; **16**: 39-45.
5. Sveger T., Liver disease in alpha1-antitrypsin deficiency detected by screening of 200,000 infants. *N Engl J Med*, 1976; **294**: 1316-21.

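### The INR dose-halving limit (1.8) lies inside the eligible entry range (up to 2.2) with no visible baseline condition, and the ALT halving and hemoglobin stopping limits carry wrong units

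*Combined protocol and SAP*

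**What the plan says.** **Entry.** Only an INR above 2.2 is excluded. The limit stands in the exclusion lists for screening and for the treatment trial, and again in the Summary, which describes disease too severe for the trial as including "serum bilirubin > 5; INR > 2.2; hepatic encephalopathy uncontrolled with outpatient medical therapy". None of these places mentions vitamin K.

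**Dose reduction.** Under *Carbamazepine (study drug) or placebo dose alteration*, the protocol states "The dose of the study drug will be altered based upon the schedule below". One line of that schedule cuts the dose by 50% when INR is at or above "1.8 not corrected by 5 mg of vitamin K". The visible line says nothing about the subject's starting value.

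**Stopping.** *Indications to discontinue CBZ* and the *Complete List of Withdrawal Criteria* both stop drug at an INR of 2.5 or more, with the same vitamin K condition.

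**General text.** *Adverse Events and Toxicity Management* says that reduction is in general unnecessary without events such as "progressive hepatic toxicity with rising transaminases, decreasing albumin levels or prolongation of the prothrombin time". *Screening and Management for Specific Adverse Events* expects INR to be raised at entry and asks that later laboratory changes be judged against each subject's own starting values.

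**Units.** The ALT halving limit is 500 in IU/dl. The ALT stop is 750 in IU/L in both lists, and the value for resuming is below 500 with no unit. The hemoglobin stop is 8.5 in mg/dl in both lists.

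**The concern.** A dose-reduction limit is meant to react to something that happens on drug. A limit that an eligible subject can already exceed at entry reacts to the disease instead. For a stable subject who entered at 1.8 to 2.2 and does not correct with vitamin K, the schedule line says halve, while the general text on progressive toxicity and baseline context says leave the dose alone. Two investigators acting in good faith could treat the same subject differently.

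The protocol makes such subjects plausible. It expects raised INR at entry, and *Screening visits* plans cover for the screening procedure: "Subjects will receive fresh frozen plasma if the INR >1.6".

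The unit slips matter because they sit in operative limits. Taken literally, one places the ALT reduction step after the ALT stop, and the other disables the hemoglobin stop, including in the list headed as complete.

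**Working it through.** The protocol gives no derived figure to reproduce here. The check compares limits and converts units.

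**1. INR entry range against the on-treatment limits**

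- Eligible at entry: INR ≤ 2.2.
- Halve: INR ≥ 1.8, uncorrected by vitamin K. Stop: INR ≥ 2.5, uncorrected by vitamin K.
- Width of the band that is both eligible and at or above the halving limit: 2.2 − 1.8 = 0.4.
- Room between entry and the stop: 2.5 − 1.8 = 0.7 for entry at 1.8, falling to 2.5 − 2.2 = 0.3 for entry at 2.2.

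**2. Is this the protocol's usual pattern?** The other numerical limits that have both an entry value and an on-treatment action are:

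| Measure | Excluded at entry | On-treatment action | Action beyond entry range? |
|---|---|---|---|
| WBC | < 1,500 | halve at < 1,000 | yes |
| Platelets | < 25,000 | halve at < 20,000 | yes |
| Total bilirubin (mg/dl) | > 5 | stop at > 7 | yes |
| Child-Pugh score | ≥ 12 | stop at > 12 | yes |
| INR (stop) | > 2.2 | stop at ≥ 2.5 | yes |
| INR (halve) | > 2.2 | halve at ≥ 1.8 | **no** |

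Only the INR halving line falls inside its own entry range.

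**3. Size of the dose change.** *Administration and Drug Accountability* says "the subjects will be started on 400 mg/day in 2 doses", with weekly steps of 200 mg/day. The first scheduled on-treatment visit is week 4 (± 1 week).

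- On the default escalation, the dose is 400 + 3 × 200 = 1,000 mg/day after three steps and 400 + 4 × 200 = 1,200 mg/day after four.
- A first halving at that visit would therefore usually be 1,000 to 500 or 1,200 to 600 mg/day. The maximum under age 15 is 1,000 mg/day, so 1,000 to 500.

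**4. ALT.** With 1 L = 10 dl, 500 IU/dl × 10 = 5,000 IU/L, and 5,000 / 750 = 6.7. As written, the fixed halving limit is 6.7 times the stopping limit, so it can never come first. Read as 500 IU/L, it sits below the 750 IU/L stop and agrees with resuming below 500.

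**5. Hemoglobin.** With 1 g = 1,000 mg, 8.5 mg/dl / 1,000 = 0.0085 g/dl. No living patient can have that value, so as written the stop cannot trigger.

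**The case against.** **The general text already governs the INR line.** Reduction is tied to progressive toxicity, changes are read against baseline, and dose changes on clinical or biochemical findings lie with the sponsor-investigator and sub-investigators: "If these individuals determine that the dose of study drug needs to be adjusted". Read together, a stable entry value is not a reason to halve, and what remains is a missing cross-reference. This carries weight and shows the probable intent. It does not settle the matter. The progressive-toxicity sentence applies only in general, the baseline sentence sits in text about what counts as an adverse event, and the sentence just quoted mainly describes how a request reaches the Study Monitor. None of them qualifies the fixed line.

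**A reader might infer that 1.8 is itself a wrong value.** The documents do not support that. A fixed, cautious limit is a legitimate choice, and the section on CBZ in liver disease expects slower elimination and perhaps a lower maintenance dose. The protocol does not give this as its reason, but the limit errs towards less drug.

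**A reader might infer that no baseline qualifier exists anywhere.** That cannot be said. The content under "Guidelines for subsequent Study drug dose adjustments" is not visible in the text reviewed, so the statement is limited to the visible line.

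**A reader might infer that ALT of 500 to 750 IU/L has no dose action.** That goes too far. The general text still allows reduction for rising transaminases, so only the fixed trigger is lost, and only on a literal reading of the unit.

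**A reader might expect a cut from 400 to 200 mg/day at the start.** With the first scheduled on-treatment visit at week 4, that is unlikely.

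**The unit slips would probably be read correctly.** This is fair. The ALT unit also appears only once and could be a fault in the text as read. The hemoglobin unit appears twice, which makes that explanation unlikely there.

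**Conclusion.** The point holds as an inconsistency in operative limits. The visible INR halving line overlaps the entry range by 0.4 units (1.8 to 2.2) and, read literally, halves the dose of a stable subject in that band who does not correct with vitamin K. The conflict with the protocol's general text is real, and none of its other paired numerical limits behaves this way.

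The size in practice is unknown. The documents give no distribution of entry INR and no rate of vitamin K correction, and the study has 30 subjects. The conclusion assumes that the content not shown under the subsequent-adjustment guidelines contains no baseline condition.

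The ALT and hemoglobin limits are unit slips with an evident intended meaning. They deserve correction because they are decision limits, but they are unlikely to mislead a clinician.

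Nothing here supports a claim of lost efficacy, altered trough levels or bias in the treatment comparison. Severity is minor to should-fix.

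**What to change.** **INR halving line.** Split it by entry value and keep the vitamin K condition in both parts.

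- Entry below 1.8: halve at INR 1.8 or more, not corrected by 5 mg of vitamin K, as now. For these subjects, reaching 1.8 is already a rise.
- Entry at 1.8 to 2.2: halve only after a rise from the subject's own baseline, not corrected by 5 mg of vitamin K. The clinical team sets the size of the rise. It must be below 0.3 for entry at 2.2, so that halving comes before the stop. A single value below 0.3 serves the whole band.
- Keep the stop at 2.5.
- Define baseline as an INR taken before any plasma given for the screening procedure.

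Simply moving the halving limit to between 2.2 and 2.5 is not advised, because it would weaken protection for subjects who enter with a near-normal INR.

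**Units.** Change the ALT halving limit to IU/L after checking the source file. Change the hemoglobin stop to g/dl in *Indications to discontinue CBZ* and in the *Complete List of Withdrawal Criteria*.

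**Cost.** The INR line is reworded, one ALT unit is changed, and the hemoglobin unit is changed in two places. The one substantive demand is that the clinical team must choose a minimum rise.
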